Check-in to trial site clinic		X														
Discharge from Clinic														X ^a		
SAFETY																
Adverse Events ^b	X	X	X	X	X	X	X	X	X	X	X	X	X	X	X	Section 8.6.1

Table 1.3-2 Schedule of Assessments - Part 2																
Period	Screening		Treatment												Follow-up Phone Call 30 (+2) days after last dose of OPC- 167832	Notes
Visit	Screening	Check-in	Period 1			Period 2										
Trial Day	-28 to -2	-1	1	2	3 to 7	8	9 and 10	11 to 13	14 to 22	23 and 24	25	26	27 to 31	32 End-of- Trial or ET		
Physical Examination ^c	X	X				X			X		X			X		Section 8.5.2
Vital Signs ^d	X	X	X	X		X	X		X		X	X		X		Section 8.5.3
Concomitant Medications	X	X	X	X	X	X	X	X	X	X	X	X	X	X	X	Section 6.5
12-Lead ECG ^e	X	X	X	X		X	X		X		X	X		X		Section 8.5.4
Laboratory Tests (hematology, serum chemistry, and urinalysis [with cell count]) ^f	X	X				X		X	X		X			X		Section 8.5.1
C-SSRS ^g	X	X												X		Section 8.5.5
IMP ADMINISTRATION																
OPC-167832			X								X					Section 6.1
Carbamazepine ^h						X	X	X	X	X	X	X	X			Section 6.1
PHARMACOKINETICS																
Blood Samples for OPC-167832 PK ⁱ			X	X	X	X					X	X	X	X		Section 8.2.1
Blood Samples for Carbamazepine PK ^j										X	X					Section 8.2.1
OTHER PROCEDURES																

CCI

Table 1.3-2 Schedule of Assessments - Part 2																
Period	Screening		Treatment												Follow-up Phone Call 30 (+2) days after last dose of OPC- 167832	Notes
Visit	Screening	Check-in	Period 1			Period 2										
Trial Day	-28 to -2	-1	1	2	3 to 7	8	9 and 10	11 to 13	14 to 22	23 and 24	25	26	27 to 31	32 End-of-Trial or ET		
Medication Compliance Evaluation			X			X	X	X	X	X	X	X	X			Section 6.4

^aAn optional in-clinic observation after the completion of the treatment period is permitted, at the discretion of the Principal Investigator. During this period of optional observation, trial participants will be kept under direct clinical observation and may have unscheduled safety procedures performed as indicated and/or as determined by site medical staff.

^bIf an adverse event suspected to be related to administration of carbamazepine is recorded, the investigator should consider performing additional hematology tests to monitor for myelosuppression.

^cComplete physical examinations will be performed at screening, predose on Days 8, 14, 25, and prior to discharge on Day 32 or at ET. A targeted physical examination will be completed at check-in and at any time per the investigator's discretion.

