2.3 Known and Potential Risks and Benefits

Subjects will receive no health benefit from participation in this trial.

Single oral doses up to 480 mg OPC-167832 were well tolerated during Trial 323-201-00001; there were no serious or severe AEs and no subjects were discontinued from the trial due to a treatment-emergent AE. One subject did decide to withdraw consent after occurrence of the nonserious and mild AEs of arthralgia, pain in extremity, and ecchymosis.¹ There was a slight negative correlation observed between changes in QT interval corrected for heart rate using Fridericia's formula (QTcF) from baseline and placebo, and OPC-167832 plasma concentrations. There is currently 1 ongoing trial (Trial 323-201-00003) that is evaluating the safety of OPC-167832 in adult subjects with uncomplicated DS pulmonary TB. There was 1 SAE of haemoptysis (3 mg group in Stage 1), which led to discontinuation of investigational medicinal product (IMP). This SAE was not considered to be causally related to the IMP but as a complication of the underlying pulmonary TB. There was 1 SAE of anal abscess (30 mg OPC-167832 and 400 mg bedaquiline group in Stage 2), which led to discontinuation of IMP and was considered unrelated to the IMP.¹

In 1-, 4-, and 26-week toxicity studies in rats, no drug-related deaths occurred in either males or females at any dose tested. Suppressed body weight gain and/or decreased food consumption were observed and increases in total cholesterol and phospholipids and decreases in creatinine were observed at 1 week. These changes showed reversibility or a tendency for reversibility.

In 1-, 4-, 13- and 39-week toxicity studies in dogs, no treatment related deaths occurred in either males or females at any dose tested. Increases in creatinine kinase, alanine aminotransferase (ALT), aspartate aminotransferase (AST), lactate dehydrogenase, and potassium were observed in the 4-week toxicity study at the highest dose (2000 mg/kg/day). Increases in total cholesterol and phospholipids were also observed in the 4- and 13-week toxicity studies at doses of 100 mg/kg/day and higher. In the 4-week toxicity study, slight prolongation of QT interval and QTc was observed at Week 4 in both sexes at 2000 mg/kg/day. However, no prolongation of QT interval and QTc was noted in the 13-week toxicity study in either sex at up to 100 mg/kg.

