10.2 Appendix 2: Clinical Laboratory Tests

The tests detailed in [Table 10.2-1](#) will be performed.

Table 10.2-1 Clinical Laboratory Assessments	
Hematology: Hemoglobin Hematocrit Mean corpuscular hemoglobin concentration Mean corpuscular volume RBC count WBC count (absolute and differential) Platelets Urinalysis: Specimen appearance Color Occult blood Glucose Microscopic analysis, if indicated, WBC/RBC counts per high powered field pH Protein Specific gravity Additional Tests: Urine or serum pregnancy for females of childbearing potential Follicle-stimulating hormone for postmenopausal females Serology (hepatitis B surface antigen, hepatitis C antibodies, human immunodeficiency virus)	Serum Chemistry: Alkaline phosphatase Alanine aminotransferase Aspartate aminotransferase Bilirubin, total (with reflex if elevated) Blood urea nitrogen Calcium Cholesterol Creatinine Gamma glutamyl transferase Glucose Lactate dehydrogenase Magnesium Potassium Protein, total Sodium Triglycerides Drug Screen (all items in urine except where noted) Alcohol Amphetamines Barbiturates Benzodiazepines Cannabinoids Cocaine Cotinine (urine or serum) Methadone Opiates Phencyclidine Propoxyphene

RBC = red blood cell; WBC = white blood cell.

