11.3 Technical Details of Pharmacokinetic Statistical Analyses

Not applicable.

12 Pharmacodynamic Analyses

Not applicable.

14 Interim Analysis

None.

Quabodepistat (OPC-167832)

Study 323-201-00007

15 Changes in Planned Analysis

None.

Quabodepistat (OPC-167832)

Study 323-201-00007

16 References

- 1 United States Department of Health and Human Services, Division of AIDS, National Institute of Allergy and Infectious Diseases, National Institutes of Health. Division of AIDS (DAIDS) Table for Grading the Severity of Adult and Pediatric Adverse Events; 2017 (version 2.1).

17 Document History

Dates/Author	Description of Updates	Version	Document Updates
26 September 2022/ CCI [REDACTED]	draft	1.0	Not Applicable
25 January 2023/ CCI [REDACTED]	draft: 
 1) updated Appendix 1. Criteria now includes only parameters relevant to the study. 2) updated Appendix 2. The entire DAIDS table has been included as Appendix 2. 3) included QTxx > 480 msec (males and females) criterion for QT, QTcF and QTcB in Appendix 5. 4) clarified collection of relatedness of adverse events to IMP and its components. 5) Other minor updates to text for greater clarity and readability. 	1.1	Applied.
13 March 2023/ CCI [REDACTED]	Final version: 1) clarifications to text	1.0	

OPC-167832

Study 323-201-00007

Appendix 1 Definition of Grades in Serum Chemistry, Hematology and Urinalysis Lab Test Results in the Division of AIDS (DAIDS) Table for Grading the Severity of Adult and Pediatric Adverse Events

The table below contains reference to the criteria provided in the DAIDS table. The DAIDS table v2.1 is attached as [Appendix 2](#) to this SAP.

Protocol Assessment	DAIDS Grading Table Row(s)	Page in DAIDS grading tables
Hematology		
Hemoglobin	Hemoglobin, Low (≥ 13 years of age (female only)	29
	Hemoglobin, Low (≥ 13 years of age (male only)	29
Hematocrit	-	-
Mean corpuscular hemoglobin concentration	-	-
Mean corpuscular volume	-	-
RBC count	-	-
WBC count (absolute and differential)	WBC, Decreased	30
Platelets	Platelets, Decreased	30
Serum Chemistry		
Alkaline phosphatase	Alkaline phosphatase, High	25
Alanine aminotransferase	ALT or SGPT, High	25
Aspartate aminotransferase	AST or SGOT, High	25
Bilirubin, total (with reflex if elevated)	Total bilirubin, High	25
Blood urea nitrogen	-	-
Calcium	Calcium, High	26
	Calcium, Low	27
	Calcium (ionized), Low	28
Cholesterol	Cholesterol, Fasting, High	27
Creatinine	Creatinine, High	26

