	Creatinine Clearance or eGFR, Low	26
Gamma glutamyl transferase	-	-
Glucose	Glucose, Fasting, High	26
	Glucose, Nonfasting, High	26
	Glucose, Low	27
Lactate dehydrogenase	Lactate, High	27
Magnesium	Magnesium, Low	27
Potassium	Potassium, Low	27

OPC-167832

Study 323-201-00007

	Potassium, High	27
Protein, total	-	-
Sodium	Sodium, High	28
	Sodium, Low	28
Triglycerides	Triglycerides, Fasting	27
Urinalysis		
Glucose or glycosuria	Glycosuria	31
Blood or hematuria	Hematuria	31
Protein or proteinuria	Proteinuria	31
Drug screen	-	-
Additional Tests		
Urine or serum pregnancy test	-	-
Follicle-stimulating hormone for post-menopausals	-	-
Serology (hepatitis B surface antigen, hepatitis C antibodies, human immunodeficiency virus)	-	-

OPC-167832

Study 323-201-00007

Appendix 2**Division of AIDS (DAIDS) Table for Grading the Severity of Adult and Pediatric Adverse Events (Corrected Version 2.1, July 2017)**

Glossary and Acronyms	
Acronym	Definition
AE	Adverse event; Any unfavorable and unintended sign (including an abnormal laboratory finding), symptom, or disease temporally associated with the use of a medical treatment or procedure regardless of whether it is considered related to the medical treatment or procedure.
ALT (SGPT)	Alanine aminotransferase (serum glutamic pyruvic transaminase)
ANC	Absolute neutrophil count
AST (SGOT)	Aspartate aminotransferase (serum glutamic-oxaloacetic transaminase)
AV	Atrioventricular
Basic Self-care Functions	Adult : Activities such as bathing, dressing, toileting, transfer or movement, continence, and feeding. Young Children : Activities that are age and culturally appropriate, such as feeding one's self with culturally appropriate eating implements.
BMI z-score	Body mass index z- score; A body reference norm. Specifically, the number of standard deviations a participant's BMI differs from the average BMI for their age, sex, and ethnicity.
BMD t-score	Bone mineral density t-score; The number of standard deviations above or below the mean bone mineral density of a healthy 30 year old adult of the same sex and ethnicity as the participant.
BMD z-score	Bone mineral density z-score; The number of standard deviations a participant's BMD differs from the average BMD for their age, sex, and ethnicity.
BPAP	Bilevel positive airway pressure; A mode used during noninvasive positive pressure ventilation.

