Glucose (mg/dL; mmol/L) Fasting, Low ≥ 1 month of age < 1 month of age	55 to 64 3.05 to < 3.55 50 to 54 2.78 to < 3.00	40 to < 55 2.22 to < 3.05 40 to < 50 2.22 to < 2.78	30 to < 40 1.67 to < 2.22 30 to < 40 1.67 to < 2.22	< 30 < 1.67 < 30 < 1.67
Lactate, High	ULN to < 2.0 × ULN without acidosis	≥ 2.0 × ULN without acidosis	Increased lactate with pH < 7.3 without life-threatening consequences	Increased lactate with pH < 7.3 with life-threatening consequences

OPC-167832

Study 323-201-00007

Chemistries				
PARAMETER	GRADE 1 MILD	GRADE 2 MODERATE	GRADE 3 SEVERE	GRADE 4 POTENTIALLY LIFE- THREATENING
Lipase, High	1.1 to < 1.5 × ULN	1.5 to < 3.0 × ULN	3.0 to < 5.0 × ULN	≥ 5.0 × ULN
Lipid Disorders (mg/dL; mmol/L)				
Cholesterol, Fasting, High ≥ 18 years of age	200 to < 240 5.18 to < 6.19	240 to < 300 6.19 to < 7.77	≥ 300 ≥ 7.77	NA
< 18 years of age	170 to < 200 4.40 to < 5.15	200 to < 300 5.15 to < 7.77	≥ 300 ≥ 7.77	NA
LDL, Fasting, High ≥ 18 years of age	130 to < 160 3.37 to < 4.12	160 to < 190 4.12 to < 4.90	≥ 190 ≥ 4.90	NA
> 2 to < 18 years of age	110 to < 130 2.85 to < 3.34	130 to < 190 3.34 to < 4.90	≥ 190 ≥ 4.90	NA
Triglycerides, Fasting, High	150 to 300 1.71 to 3.42	> 300 to 500 > 3.42 to 5.7	> 500 to < 1,000 > 5.7 to 11.4	> 1,000 > 11.4
Magnesium, Low (mEq/L; mmol/L)	1.2 to < 1.4 0.60 to < 0.70	0.9 to < 1.2 0.45 to < 0.60	0.6 to < 0.9 0.30 to < 0.45	< 0.6 < 0.30
Phosphate, Low (mg/dL; mmol/L)				
> 14 years of age	2.0 to < LLN 0.65 to < LLN	1.4 to < 2.0 0.45 to < 0.65	1.0 to < 1.4 0.32 to < 0.45	< 1.0 < 0.32
1 to 14 years of age	3.0 to < 3.5 0.97 to < 1.13	2.5 to < 3.0 0.81 to < 0.97	1.5 to < 2.5 0.48 to < 0.81	< 1.5 < 0.48
< 1 year of age	3.5 to < 4.5 1.13 to < 1.45	2.5 to < 3.5 0.81 to < 1.13	1.5 to < 2.5 0.48 to < 0.81	< 1.5 < 0.48
Potassium, High (mEq/L; mmol/L)	5.6 to < 6.0 5.6 to < 6.0	6.0 to < 6.5 6.0 to < 6.5	6.5 to < 7.0 6.5 to < 7.0	≥ 7.0 ≥ 7.0
Potassium, Low (mEq/L; mmol/L)	3.0 to < 3.4 3.0 to < 3.4	2.5 to < 3.0 2.5 to < 3.0	2.0 to < 2.5 2.0 to < 2.5	< 2.0 < 2.0
Sodium, High (mEq/L; mmol/L)	146 to < 150 146 to < 150	150 to < 154 150 to < 154	154 to < 160 154 to 160	> 160 > 160
Sodium, Low (mEq/L; mmol/L)	130 to < 135 130 to < 135	125 to < 130 125 to < 130	121 to < 125 121 to < 125	< 120 < 120
Uric Acid, High (mg/dL; mmol/L)	7.5 to < 10.0 0.45 to < 0.59	10.0 to < 12.0 0.59 to < 0.71	12.0 to < 15.0 0.71 to < 0.89	> 15.0 > 0.89

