a Direct bilirubin > 1.5 mg/dL in a participant < 28 days of age should be graded as grade 2, if < 10% of the total bilirubin.

b Use the applicable formula (ie, Cockcroft-Gault in mL/min or Schwartz, MDRD, CKD-Epi in mL/min/1.73m²). Sites should choose the method defined in their study and when not specified, use the method most relevant to the study population.

c To convert a magnesium value from mg/dL to mmol/L, laboratories should multiply by 0.4114.

OPC-167832

Study 323-201-00007

Hematology				
PARAMETER	GRADE 1 MILD	GRADE 2 MODERATE	GRADE 3 SEVERE	GRADE 4 POTENTIALLY LIFE- THREATENING
Absolute CD4+ Count, Low (cell/mm ³ ; cells/L) > 5 years of age (not HIV infected)	300 to < 400 300 to < 400	200 to < 300 200 to < 300	100 to < 200 100 to < 200	< 100 < 100
Absolute Lymphocyte Count, Low (cell/mm ³ ; cells/L) > 5 years of age (not HIV infected)	600 to < 650 0.600×10^9 to < 0.650×10^9	500 to < 600 0.500×10^9 to < 0.600×10^9	350 to < 500 0.350×10^9 to < 0.500×10^9	< 350 < 0.350×10^9
Absolute Neutrophil Count (ANC), Low (cells/mm ³ ; cells/L) > 7 days of age 2 to 7 days of age ≤ 1 day of age	800 to 1,000 0.800×10^9 to 1.000×10^9 1,250 to 1,500 1.250×10^9 to 1.500×10^9 4,000 to 5,000 4.000×10^9 to 5.000×10^9	600 to 799 0.600×10^9 to 0.799×10^9 1,000 to 1,249 1.000×10^9 to 1.249×10^9 3,000 to 3,999 3.000×10^9 to 3.999×10^9	400 to 599 0.400×10^9 to 0.599×10^9 750 to 999 0.750×10^9 to 0.999×10^9 1,500 to 2,999 1.500×10^9 to 2.999×10^9	< 400 < 0.400×10^9 < 750 < 0.750×10^9 < 1,500 < 1.500×10^9
Fibrinogen, Decreased (mg/dL; g/L)	100 to < 200 1.00 to < 2.00 OR 0.75 to < $1.00 \times \text{LLN}$	75 to < 100 0.75 to < 1.00 OR ≥ 0.50 to < $0.75 \times \text{LLN}$	50 to < 75 0.50 to < 0.75 OR 0.25 to < $0.50 \times \text{LLN}$	< 50 < 0.50 OR < $0.25 \times \text{LLN}$ OR Associated with gross bleeding

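### SAP Appendix 1 grades lactate dehydrogenase with the DAIDS row for lactate, and its entry for the white-cell differential omits the neutrophil row printed in Appendix 2

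*SAP*

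**What the plan says.** SAP Appendix 1 lists each protocol laboratory test with the DAIDS row that grades it and the page of that row. Two entries matter here.

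- Serum chemistry: "Lactate dehydrogenase Lactate, High 27".
- Hematology: "WBC count (absolute and differential) WBC, Decreased 30".

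SAP Appendix 2 reprints the whole DAIDS table. In its chemistry section, Grades 1 and 2 for lactate are multiples of the ULN in the absence of acidosis. Grade 3 reads "Increased lactate with pH < 7.3 without life-threatening consequences", and Grade 4 adds life-threatening consequences. The reprinted table has no LDH row. Its hematology section has a row headed "Absolute Neutrophil Count (ANC), Low", a lymphocyte row, and the total WBC row.

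SAP 10.3 points to both appendices. It names Appendix 2 as the place where the criteria for potentially clinically relevant laboratory abnormalities are found, then says that the DAIDS grading tables will be used in addition, citing Appendix 1. It does not say which prevails if they differ.

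Protocol Table 10.2-1 lists LDH under serum chemistry and the white-cell differential under hematology. It lists no lactate, and the only pH is under urinalysis.

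**The concern.** The LDH entry borrows cut-offs written for another substance, and those cut-offs depend on a measurement that the trial does not make. LDH is not an idle member of the panel. Protocol 2.3 reports for dogs: "Increases in creatinine kinase, alanine aminotransferase (ALT), aspartate aminotransferase (AST), lactate dehydrogenase, and potassium were observed in the 4-week toxicity study", at the highest dose.

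The differential entry looks like an omission rather than a convention, because Appendix 1 cites several rows where several apply: three each for calcium and glucose, two each for potassium and sodium. The SAP's document history says that Appendix 1 was cut down to parameters relevant to the study, so a programmer could read the missing neutrophil row as a decision that neutrophils are not relevant. The protocol treats them as relevant in Part 2. Exclusion criterion 25 rejects subjects with neutrophils below the lower limit of normal. Footnote b to Table 1.3-2 says that, if an adverse event suspected to be related to carbamazepine is recorded, "the investigator should consider performing additional hematology tests to monitor for myelosuppression".

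At stake is the planned incidence summary of potentially clinically significant laboratory abnormalities. It serves the secondary objective of safety and tolerability.

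**Working it through.** The plan states no figure to reproduce. The check sets the two appendices beside the protocol panel and applies the printed cut-offs to assumed values.

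**LDH.** Inputs: Appendix 1 entry; Appendix 2 lactate row; Protocol Table 10.2-1.

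| Grade in lactate row | Multiple of ULN | Further condition | Can this trial's data confirm it? |
|---|---|---|---|
| 1 | 1 to < 2.0 | no acidosis | No, blood pH is not measured |
| 2 | ≥ 2.0 | no acidosis | No, same reason |
| 3 | increased | pH < 7.3 | No |
| 4 | increased | pH < 7.3, life-threatening | No |

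Taken strictly, no grade in the row can be confirmed. If a programmer reads missing pH as no acidosis, LDH of 1.5 × ULN becomes Grade 1, and 2 × ULN or any higher multiple, including 10 × ULN, becomes Grade 2. Grades 3 and 4 remain out of reach at any LDH value.

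Appendix 1 has its own convention for tests without a DAIDS row: gamma glutamyl transferase, blood urea nitrogen, total protein and hematocrit carry a dash. LDH belongs in that group but does not follow the convention.

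**Neutrophils.** Inputs: adult cut-offs in Appendix 2, in cells/mm³.

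| Row | Grade 1 | Grade 2 | Grade 3 | Grade 4 |
|---|---|---|---|---|
| ANC | 800–1,000 | 600–799 | 400–599 | < 400 |
| WBC | 2,000–2,499 | 1,500–1,999 | 1,000–1,499 | < 1,000 |

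ANC = WBC × neutrophil share. With assumed values:

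- 2,600 × 0.25 = 650: ANC Grade 2, WBC ungraded.
- 2,600 × 0.20 = 520: ANC Grade 3, WBC ungraded.
- 3,000 × 0.12 = 360: ANC Grade 4, WBC ungraded.

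For any WBC of 2,500 or more, the WBC row is silent whenever the neutrophil share is at or below 1,000/WBC. At WBC 2,500 that share is 1,000/2,500 = 40%; at 3,000 it is 1,000/3,000 = 33%. These cases show that total WBC cannot stand in for ANC. They do not show how often this would happen.

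**How often LDH might be graded, for scale only.** Expected Grade 1 or higher LDH values in Part 1 = subjects × draws × share of values above ULN. Table 1.3-1 schedules laboratory tests after the Day −1 baseline on Days 1, 2, 15, 16 and 26. The documents give no share; assume 2.5%. Then 12 × 5 × 0.025 = 1.5. The table does not say whether the Day 1 draw is predose; without it, 12 × 4 × 0.025 = 1.2. Halving the share with four draws gives 12 × 4 × 0.0125 = 0.6, and doubling it with five draws gives 12 × 5 × 0.05 = 3.0. All of this also assumes that missing pH is read as no acidosis.

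**The case against.** The strongest reply concerns neutrophils. A reader might infer that they are not graded at all. The documents do not support that. SAP 10.3 names Appendix 2 as the criteria source and cites Appendix 1 only in addition, and Appendix 2 prints the adult ANC and lymphocyte rows. A programmer working from Appendix 2 would grade ANC. This stands, and it reduces the neutrophil half to an incomplete map and an unresolved choice between two appendices.

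A reader might also infer that neutropenia would go unnoticed. That goes too far as well. SAP 10.3 summarizes laboratory parameters and their changes from baseline, and lists the investigator's assessment of abnormal values. Under Protocol 8.5.1 and 8.6.1 the investigator reviews each laboratory report, and clinically significant values are recorded as adverse events. Part 2 samples are taken predose on Days 8, 11, 14 and 25 and before discharge on Day 32.

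A third inference would be that the tables would report a lactate abnormality. No text says that output would carry that label. Appendix 1 names the test as LDH and takes only the cut-offs from the lactate row, and SAP 10.3 summarizes by test. The supportable claim is that the cut-offs are wrong for the analyte.

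The relevance of LDH should not be inflated either. The dog finding was at 2000 mg/kg/day in the 4-week study and came with rises in ALT and AST, both of which Appendix 1 maps correctly. This trial gives two single 30-mg doses.

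None of this repairs the LDH entry. Appendix 2 has no LDH row, so following it leaves LDH ungraded while following Appendix 1 gives it lactate grades. Nothing tells the programmer to set the Appendix 1 entry aside.

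**Conclusion.** The LDH entry is wrong as written. Followed literally, it applies another analyte's criteria, and Grades 3 and 4 cannot be assigned whatever the LDH value. That rests only on the two appendices and the protocol's test list.

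For neutrophils, the defect is an incomplete entry in Appendix 1 together with no statement of which appendix governs. The SAP as it stands permits two different tables of neutrophil abnormalities, one of which has no ANC grades. The WBC and neutrophil values used to show the gap are illustrative, and Part 2 subjects must not have WBC or neutrophil counts below the lower limit of normal at entry.

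The impact is confined to descriptive safety summaries. The analysis of C_max, AUC_t and AUC_∞ is untouched. The count of about one LDH grade in Part 1 (0.6 to 3.0 over the range shown) depends on an assumed rate and carries no weight in this conclusion. The correction is worth making because it is cheap and the error is plain.

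**What to change.** Make three changes in the SAP.

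1. Appendix 1, LDH: replace the lactate row and page with a dash, as for gamma glutamyl transferase and blood urea nitrogen. A separate LDH criterion, reported as LDH, is optional; if the sponsor wants one, its threshold should be stated before the tables are produced.
2. Appendix 1, differential: add the ANC row with its page. Add the lymphocyte row for completeness; the protocol gives no specific reason for it.
3. SAP 10.3: add one sentence saying which appendix governs laboratory grading where the two differ.

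The cost is a few cells in one appendix table and one sentence, with the matching change to the laboratory table programs. No new data are needed, since LDH and the differential are already collected.

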Appendix Usage

Appendix A takes priority over the main grading table in all assessments of total bilirubin for term and preterm neonates.

Using Addenda 1-3: Grading Tables Used in Microbicide Studies

In protocols involving topical application of products to the female and male genital tracts or rectum, strong consideration should be given to using Addenda 1-3 (see below) as the primary grading tables for these areas. Although these grading tables are used specifically in microbicide studies, they may be used in other protocols as adjuncts to the main grading table (ie, the *Division of AIDS (AIDS) Table for Grading the Severity of Adult and Pediatric Adverse Events, Version 2.0*). It should be clearly stated in a protocol which addendum is being used as the primary grading table (and thus takes precedence over the main grading table) and which addendum is being used in a complementary fashion.

- Addendum 1 – Female Genital Grading Table for Use in Microbicide Studies – <http://rsc.tech-res.com/clinical-research-sites/safety-reporting/daids-grading-tables>
- Addendum 2 – Male Genital Grading Table for Use in Microbicide Studies – <http://rsc.tech-res.com/clinical-research-sites/safety-reporting/daids-grading-tables>
- Addendum 3 – Rectal Grading Table for Use in Microbicide Studies – <http://rsc.tech-res.com/clinical-research-sites/safety-reporting/daids-grading-tables>

Estimating Severity Grade for Parameters Not Identified in the Grading Table

The functional table below should be used to grade the severity of an AE that is not specifically identified in the grading table. In addition, all deaths related to an AE are to be classified as grade 5.

OPC-167832

Study 323-201-00007

Estimating Severity Grade for Parameters Not Identified in the Grading Table				
PARAMETER	GRADE 1 MILD	GRADE 2 MODERATE	GRADE 3 SEVERE	GRADE 4 POTENTIALLY LIFE- THREATENING
Clinical adverse event NOT identified elsewhere in the grading table	Mild symptoms causing no or minimal interference with usual social & functional activities with intervention not indicated	Moderate symptoms causing greater than minimal interference with usual social & functional activities with intervention indicated	Severe symptoms causing inability to perform usual social & functional activities with intervention or hospitalization indicated	Potentially life-threatening symptoms causing inability to perform basic self-care functions with intervention indicated to prevent permanent impairment, persistent disability, or death

Study 323-201-00007

Cardiovascular				
PARAMETER	GRADE 1 MILD	GRADE 2 MODERATE	GRADE 3 SEVERE	GRADE 4 POTENTIALLY LIFE- THREATENING
Arrhythmia (by ECG or physical examination) Specify type, if applicable	No symptoms AND No intervention indicated	No symptoms AND Non-urgent intervention indicated	Non-life-threatening symptoms AND Non-urgent intervention indicated	Life-threatening arrhythmia OR Urgent intervention indicated
Blood Pressure Abnormalities^a Hypertension (with the lowest reading taken after repeat testing during a visit) 
 
≥ 18 years of age
 
 
140 to < 160 mmHg systolic
 
OR
 
90 to < 100 mmHg diastolic
 
 
 
 
< 18 years of age
 
> 120/80 mmHg
 
	
 
≥ 160 to < 180 mmHg systolic
 
OR
 
≥ 100 to < 110 mmHg diastolic
 
 
 
≥ 95th to < 99th percentile + 5 mmHg adjusted for age, height, and gender (systolic and/or diastolic)
 
	
 
≥ 180 mmHg systolic
 
OR
 
≥ 110 mmHg diastolic
 
 
 
≥ 99th percentile + 5 mmHg adjusted for age, height, and gender (systolic and/or diastolic)
 
	
 
Life-threatening consequences in a participant not previously diagnosed with hypertension (eg, malignant hypertension)
 
OR hospitalization indicated
 
 
 
Life-threatening consequences in a participant not previously diagnosed with hypertension (eg, malignant hypertension)
 
OR hospitalization indicated
 
	
Hypotension	No symptoms	Symptoms corrected with oral fluid replacement	Symptoms AND IV fluids indicated	Shock requiring use of vasopressors or mechanical assistance to maintain blood pressure

OPC-167832

Study 323-201-00007

Cardiovascular				
PARAMETER	GRADE 1 MILD	GRADE 2 MODERATE	GRADE 3 SEVERE	GRADE 4 POTENTIALLY LIFE- THREATENING
Cardiac Ischemia or Infarction Report only one	NA	NA	New symptoms with ischemia (stable angina) OR New testing consistent with ischemia	Unstable angina OR Acute myocardial infarction
Heart Failure	No symptoms AND Laboratory or cardiac imaging abnormalities	Symptoms with mild to moderate activity or exertion	Symptoms at rest or with minimal activity or exertion (eg, hypoxemia) OR Intervention indicated (eg, oxygen)	Life-threatening consequences OR Urgent intervention indicated (eg, vasoactive medications, ventricular assist device, heart transplant)
Hemorrhage (with acute significant blood loss) > 16 years of age ≤ 16 years of age	PR interval 0.21 to < 0.25 seconds 1st degree AV block (PR interval > normal for age and rate)	PR interval ≥ 0.25 seconds OR Type I 2nd degree AV block Type I 2nd degree AV block	Type II 2nd degree AV block OR Ventricular pause ≥ 3.0 seconds Type II 2nd degree AV block OR Ventricular pause ≥ 3.0 seconds	Complete AV block Complete AV block
Prolonged QTc Interval^b	0.45 to 0.47 seconds	> 0.47 to 0.50 seconds	> 0.50 seconds OR ≥ 0.06 seconds above baseline	Life-threatening consequences (eg, Torsade de pointes, other associated serious ventricular dysrhythmia)
Thrombosis or Embolism Report only one	NA	Symptoms AND No intervention indicated	Symptoms AND Intervention indicated	Life-threatening embolic event (eg, pulmonary embolism, thrombus)

a Blood pressure norms for children < 18 years of age can be found in: Expert Panel on Integrated Guidelines for Cardiovascular Health and Risk Reduction in Children and Adolescents. *Pediatrics* 2011;128;S213; originally published online November 14, 2011; DOI: 10. 1542/peds.2009-2107C.

b As per Bazett's formula.

OPC-167832

Study 323-201-00007

Dermatologic				
PARAMETER	GRADE 1 MILD	GRADE 2 MODERATE	GRADE 3 SEVERE	GRADE 4 POTENTIALLY LIFE- THREATENING
Alopecia (scalp only)	Detectable by study participant, caregiver, or physician AND Causing no or minimal interference with usual social & functional activities	Obvious on visual inspection AND Causing greater than minimal interference with usual social & functional activities	NA	NA
Bruising	Localized to one area	Localized to more than one area	Generalized	NA
Cellulitis	NA	Non-parenteral treatment indicated (eg, oral antibiotics, antifungals, antivirals)	IV treatment indicated (eg, IV antibiotics, antifungals, antivirals)	Life-threatening consequences (eg, sepsis, tissue necrosis)
Hyperpigmentation	Slight or localized causing no or minimal interference with usual social & functional activities	Marked or generalized causing greater than minimal interference with usual social & functional activities	NA	NA
Hypopigmentation	Slight or localized causing no or minimal interference with usual social & functional activities	Marked or generalized causing greater than minimal interference with usual social & functional activities	NA	NA
Petechiae	Localized to one area	Localized to more than one area	Generalized	NA
Pruritus (without skin lesions)	Itching causing no or minimal interference with usual social & functional activities	Itching causing greater than minimal interference with usual social & functional activities	Itching causing inability to perform usual social & functional activities	NA

OPC-167832

Study 323-201-00007

Dermatologic				
PARAMETER	GRADE 1 MILD	GRADE 2 MODERATE	GRADE 3 SEVERE	GRADE 4 POTENTIALLY LIFE- THREATENING
Rash Specify type, if applicable	Localized rash	Diffuse rash OR Target lesions	Diffuse rash AND Vesicles or limited number of bullae or superficial ulcerations of mucous membrane limited to one site	Extensive or generalized bullous lesions OR Ulceration of mucous membrane involving two or more distinct mucosal sites OR Stevens-Johnson syndrome OR Toxic epidermal necrolysis

a For pruritus associated with injections or infusions, see the *Site Reactions to Injections and Infusions* section.

OPC-167832

Study 323-201-00007

Endocrine and Metabolic				
PARAMETER	GRADE 1 MILD	GRADE 2 MODERATE	GRADE 3 SEVERE	GRADE 4 POTENTIALLY LIFE- THREATENING
Diabetes Mellitus	Controlled without medication	Controlled with medication OR Modification of current medication regimen	Uncontrolled despite treatment modification OR Hospitalization for immediate glucose control indicated	Life-threatening consequences (eg, ketoacidosis, hyperosmolar non-ketotic coma, end organ failure)
Gynecomastia	Detectable by study participant, caregiver, or physician AND Causing no or minimal interference with usual social & functional activities	Obvious on visual inspection AND Causing pain with greater than minimal interference with usual social & functional activities	Disfiguring changes AND Symptoms requiring intervention or causing inability to perform usual social & functional activities	NA
Hyperthyroidism	No symptoms AND Abnormal laboratory value	Symptoms causing greater than minimal interference with usual social & functional activities OR Thyroid suppression therapy indicated	Symptoms causing inability to perform usual social & functional activities OR Uncontrolled despite treatment modification	Life-threatening consequences (eg, thyroid storm)
Hypothyroidism	No symptoms AND Abnormal laboratory value	Symptoms causing greater than minimal interference with usual social & functional activities OR Thyroid replacement therapy indicated	Symptoms causing inability to perform usual social & functional activities OR Uncontrolled despite treatment modification	Life-threatening consequences (eg, myxedema coma)
Lipoatrophy^a	Detectable by study participant, caregiver, or physician AND Causing no or minimal interference with usual social & functional activities	Obvious on visual inspection AND Causing greater than minimal interference with usual social & functional activities	Disfiguring changes	NA

OPC-167832

Study 323-201-00007

Endocrine and Metabolic				
PARAMETER	GRADE 1 MILD	GRADE 2 MODERATE	GRADE 3 SEVERE	GRADE 4 POTENTIALLY LIFE- THREATENING
Lipohypertrophy^b	Detectable by study participant, caregiver, or physician AND Causing no or minimal interference with usual social & functional activities	Obvious on visual inspection AND Causing greater than minimal interference with usual social & functional activities	Disfiguring changes	NA

a Definition: A disorder characterized by fat loss in the face, extremities, and buttocks.

b Definition: A disorder characterized by abnormal fat accumulation on the back of the neck, breasts, and abdomen.

OPC-167832

Study 323-201-00007

Gastrointestinal				
PARAMETER	GRADE 1 MILD	GRADE 2 MODERATE	GRADE 3 SEVERE	GRADE 4 POTENTIALLY LIFE- THREATENING
Anorexia	Loss of appetite without decreased oral intake	Loss of appetite associated with decreased oral intake without significant weight loss	Loss of appetite with significant weight loss	Life-threatening consequences OR Aggressive intervention (eg, tube feeding, total parenteral nutrition)
Ascites	No symptoms	Symptoms AND Intervention indicated (eg, diuretics, therapeutic paracentesis)	Symptoms recur or persist despite intervention	Life-threatening consequences
Bloating or Distension Report only one	Symptoms causing no or minimal interference with usual social & functional activities	Symptoms causing greater than minimal interference with usual social & functional activities	Symptoms causing inability to perform usual social & functional activities	NA
Cholecystitis	NA	Symptoms AND Medical intervention indicated	Radiologic, endoscopic, or operative intervention indicated	Life-threatening consequences (eg, sepsis, perforation)
Constipation	NA	Persistent constipation requiring regular use of dietary modifications, laxatives, or enemas	Obstipation with manual evacuation needed	Life-threatening consequences (eg, obstruction)
Diarrhea ≥ 1 year of age < 1 year of age	Transient or intermittent episodes of unformed stools OR Increase of ≤ 3 stools over baseline per 24 hour period Liquid stools (more unformed than usual) but usual number of stools	Persistent episodes of unformed to watery stools OR Increase of 4 to 6 stools over baseline 24 hour period Liquid stools with increased number of stools OR Mild dehydration	Increase of ≥ 7 stools per 24 hour period OR IV fluid replacement indicated Liquid stools with moderate dehydration	Life-threatening consequences (eg, hypotensive shock) Life-threatening consequences (eg, liquid stools resulting in severe dehydration, hypotensive shock)

OPC-167832

Study 323-201-00007

Gastrointestinal				
PARAMETER	GRADE 1 MILD	GRADE 2 MODERATE	GRADE 3 SEVERE	GRADE 4 POTENTIALLY LIFE- THREATENING
Dysphagia or Odynophagia Report only one and specify location	Symptoms but able to eat usual diet	Symptoms causing altered dietary intake with no intervention indicated	Symptoms causing severely altered dietary intake with intervention indicated	Life-threatening reduction in oral intake
Gastrointestinal Bleeding	Not requiring intervention other than iron supplement	Endoscopic intervention indicated	Transfusion indicated	Life-threatening consequences (eg, hypotensive shock)
Mucositis or Stomatitis Report only one and specify location	Mucosal erythema	Patchy pseudomembranes or ulcerations	Confluent pseudomembranes or ulcerations OR Mucosal bleeding with minor trauma	Life-threatening consequences (eg, aspiration, choking) OR Tissue necrosis OR Diffuse spontaneous mucosal bleeding
Nausea	Transient (< 24 hours) or intermittent AND No or minimal interference with oral intake	Persistent nausea resulting in decreased oral intake for 24 to 48 hours	Persistent nausea resulting in minimal oral intake for > 48 hours OR Rehydration indicated (eg, IV fluids)	Life-threatening consequences (eg, hypotensive shock)
Pancreatitis	NA	Symptoms with hospitalization not indicated	Symptoms with hospitalization indicated	Life-threatening consequences (eg, circulatory failure, hemorrhage, sepsis)
Perforation (colon or rectum)	NA	NA	Intervention indicated	Life-threatening consequences
Proctitis	Rectal discomfort with no intervention indicated	Symptoms causing greater than minimal interference with usual social & functional activities OR Medical intervention indication	Symptoms causing inability to perform usual social & functional activities OR Operative intervention indicated	Life-threatening consequences (eg, perforation)
Rectal Discharge	Visible discharge	Discharge requiring the use of pads	NA	NA

OPC-167832

Study 323-201-00007

Gastrointestinal				
PARAMETER	GRADE 1 MILD	GRADE 2 MODERATE	GRADE 3 SEVERE	GRADE 4 POTENTIALLY LIFE- THREATENING
Vomiting	Transient or intermittent AND No or minimal interference with oral intake	Frequent episodes with no or mild dehydration	Persistent vomiting resulting in orthostatic hypotension OR Aggressive rehydration indicated (eg, IV fluids)	Life-threatening consequences (eg, hypotensive shock)

OPC-167832

Study 323-201-00007

Musculoskeletal				
PARAMETER	GRADE 1 MILD	GRADE 2 MODERATE	GRADE 3 SEVERE	GRADE 4 POTENTIALLY LIFE- THREATENING
Arthralgia	Joint pain causing no or minimal interference with usual social & functional activities	Joint pain causing greater than minimal interference with usual social & functional activities	Joint pain causing inability to perform usual social & functional activities	Disabling joint pain causing inability to perform basic self-care functions
